grounds decision prior to entry into NGO support, though this is not always the case. Individuals who have entered NGO support prior to receiving a reasonable grounds decision who then receive a negative decision are exited from support services.

A second "conclusive grounds" decision regarding an individual's claim to have been trafficked will then be made. The target for decision-making is 45 days, though in practice the decision-making period is often longer. An individual who receives a negative conclusive grounds decision is determined not to be a victim of trafficking, and is exited from support services. Individuals who receive a positive conclusive grounds decision can continue to receive NGO support services; the default support period in England and Wales is 45 days. Individuals can, however, apply to extend their access to support services by up to 6 months (renewable) via the Recovery Needs Assessment process.

Prior to intake, an Initial Assessment will be completed in order to determine eligibility, risk, and urgent needs. Individuals who lack mental capacity, who have severe drug and alcohol problems, or who are acutely mentally unwell are not supported by the NGO services. After arrival at NGO services, a Detailed Needs Based Assessment is undertaken, followed by an Individual Support Plan. The intervention is considered to commence at the initiation of the individual support planning process. The support plan is individualised but organised according to the following categories:

- 1. Secure and appropriate accommodation
- 2. Provision of subsistence payments
- 3. Access to emergency health services
- 4. Advocacy for specialist services
- 5. Assistance with criminal proceedings
- 6. Access to education for dependent school age children
- 7. Access to compensation

These categories align to the entitlements of survivors of trafficking under the Council of Europe Convention on Action Against Trafficking in Human Beings (ECAT) rather than to advocacy activity categories described by the initial programme theory.

Other concomitant care and interventions are permitted during the trial (e.g. psychological interventions); data on receipt of other health and social care services are collected (see section 12, outcomes).

12. Outcomes

Study 1 – Cohort Study

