Outcomes align with the initial programme theory for the advocacy intervention developed in collaboration with NGOs and informed by relevant literature. Commonly-used, well-validated measures have been chosen where these exist for the outcome of interest and items are relevant to the experiences of trafficking survivors.

Primary outcome

The primary outcome is psychological distress at T2 versus T1. Psychological distress will be measured by the Clinical Outcomes in Routine Evaluation- Outcome Measure (CORE-OM), a 34-item questionnaire which measures global psychological distress. The questionnaire was

designed to assess efficacy and effectiveness across multiple disciplines offering psychological therapies (19). It has good internal and test-retest reliability (0.75-0.95), large differences between clinical and non-clinical samples, and good sensitivity to change (19). Validation work in general population samples shows the CORE-ORM is highly correlated (r=0.77) with the Clinical Interview Schedule-Revised (CISR), supporting convergent validity (20). It has good acceptability in domestic violence research (21, 22) and has been used in research with survivors of human trafficking (23).

Secondary outcomes

Secondary outcomes are CORE-OM score at T3, and health-related quality of life, social support, unmet needs, perceived safety and risk of harm, autonomy, and use of health and social care services at T2 and T3.

- 1. **Health-related quality of life** will be measured using the EQ-5D-5L and SF-12 (25, 26) and the Recovering Quality of Life-10 (ReQoL-10) (27), a new 10-item Patient Reported Outcome Measure (PROM) that has been developed to assess the quality of life for users of mental health services.
- 2. Use of health and social care services will be measured using an adapted version of the Adult Service Use Schedule (AD-SUS) (24). The AD-SUS is a structured instrument which collects data on participants' use of health and social care services for the three-months preceding interview (at baseline) or since the previous interview (at any follow-up point).

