Interviews with staff will explore, for example views about the type of support provided, the ways in which programme components are implemented, the way change is facilitated, current organisational practice and culture, local and national context of trafficking support provision, enabling and constraining factors (contextual factors); what does and does not help survivors and why (mechanisms); and perceived changes in the mental health and wellbeing of service users (outcomes).

13. Participant timeline

The baseline questionnaire (T1) will take place after commencement of individual support planning (i.e. start of intervention) and within two weeks of intake into NGO support services (for clients receiving residential advocacy support) or within 4 weeks of intake (for clients receiving outreach advocacy support).

Follow-up comprises completion of questionnaires at 3 months' follow-up (T2) and at 6 months' follow-up (T3). A 28 day window, defined as 7 days before and 21 days after the due date, will be available to complete the T2 and T3 follow up interviews. Participants who do not complete T2 and T3 interviews with the defined window will be considered to have missed that data collection point. Participants who do not complete T2 interviews will remain eligible to participate at T3.

The data collection timetable is as follows

Research data type	Form name	T1 (Baseli ne)	T2 Follow Up (+90 days)	T3 Follow Up (+180 days)	Ongoing	End of Study
Baseline characteristics	1. Registration Form	X				
Baseline characteristics	2. Eligibility	X				
Baseline characteristics	3. Trafficking-Related Characteristics	X				
Baseline characteristics	5. Immigration and Housing Status	X	X	X		
Primary outcome	6. CORE-OM	X	X	X		
Secondary outcome	7. EQ-5D-5L	X	X	X		
Secondary outcome	8. SF-12	X	X	X		
Secondary outcome	9. ReQoL-10	X	X	X		
Secondary outcome	11. Adapted AD-SUS	X	X	X		
Secondary outcome	12. Adapted PMLDC	X	X	X		
Secondary outcome	13. Adapted SSN	X	X	X		
Secondary outcome	14. Adapted IPV Threat Appraisal and Fear Scale	X	X	X		
Secondary outcome	15. Autonomy	X	X	X		
Process variables	16. Advocacy Support Attendance Log				X	
CONSORT data	4. Status Form		X	X		
CONSORT data	17. Withdrawal Form				X	
-	18. PI Sign Off					X

14. Sample size

Study 1 – Cohort Study

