- 2. Develop and test an appropriately adapted version of the AD-SUS to collect data on the use of all health and social care services (taking the NHS/personal social services perspective preferred by NICE) and use this data to estimate the cost per participant through the application of nationally applicable unit costs (39).
- 3. Assess whether receipt of advocacy support is associated with changes in service use and costs (i.e. before and after intervention).
- 4. Test the acceptability and relevance of preference-based measures of health-related
- 5. quality of life (HRQoL) for the current population, including the EQ-5D-5L (EuroQol 5 dimensions, 5 levels), the SF-6D (Short Form 6 dimensions), and the ReQoL-10, which are all capable of generating quality adjusted life years (QALYs) suitable for future economic evaluations (25, 27, 40).
- 6. In line with the proposed clinical analyses noted above, explore whether receipt of advocacy support is associated with improvements in HRQoL and QALYs and whether change over time varies with participant characteristics at baseline or with the structural or service characteristics of NGOs.

22. Qualitative analysis

Analysis of qualitative data collected in study 2 will support the testing of initial programme theory using empirical data and the refinement of programme theory. This will involve moving iteratively between case analysis, refinement of programme theory, and further data collection to test emerging theory about how advocacy interventions improve outcomes, for whom, and under what circumstances. The coding of qualitative data will be inductive, deductive, and

retroductive (i.e. informed by theory, emerging from the data, and making inferences about mechanisms based on interpretations of the data).

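### The baseline service-use period runs back from an interview held after support has begun, so the before part of the before-and-after cost comparison contains post-intake days that a single total cannot separate

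*Protocol*

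**What the plan says.** Protocol section 12 (secondary outcome 2) has the adapted AD-SUS collect use of health and social care services "for the three-months preceding interview (at baseline) or since the previous interview (at any follow-up point").

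Three other sections fix what that period contains:

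- **Section 11, start of the intervention:** "The intervention is considered to commence at the initiation of the individual support planning process".
- **Section 13, timing of T1:** the baseline questionnaire follows the start of support planning, which is glossed there as the start of the intervention. It must fall within two weeks of intake for residential clients or four weeks for outreach clients. Inclusion criterion 4 in section 10 sets nearly the same limits (fewer than 14 or 28 days of support).
- **Section 13, follow-up:** T2 and T3 are due at +90 and +180 days. The section gives "A 28 day window, defined as 7 days before and 21 days after the due date", and adds: "Participants who do not complete T2 interviews will remain eligible to participate at T3".

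Section 21, objective 3, states the comparison: "Assess whether receipt of advocacy support is associated with changes in service use and costs (i.e. before and after intervention"). The same section calls the economic analysis exploratory, presents it as cost-consequences, and costs advocacy separately by micro-costing.

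**The concern.** By the protocol's own definitions, T1 lies inside the intervention. A recall period that runs back from T1 therefore ends inside the intervention too, yet it serves as the before side of the comparison in section 21.

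This matters because the support plan in section 11 includes access to emergency health services and advocacy for specialist services. That is the kind of contact the AD-SUS counts. If such contacts change soon after intake, some of the change is booked as baseline and the comparison is diluted. The possible dilution is larger for outreach clients, because their interview may fall later.

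The anchor of the recall question is settled when data are collected. As section 12 describes the instrument, it yields use over one period, and an analysis plan cannot divide that total at intake afterwards.

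A second, lesser matter is that recall since the previous interview varies in length with the visit window and roughly doubles when T2 is missed.

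**Working it through.** **Inputs.** Baseline recall of three months (section 12). Maximum time from intake to T1 of 14 days residential and 28 days outreach (section 13). T2 at +90 and T3 at +180 days, each −7/+21 days (section 13). Assumptions: three months = 90 days, and due dates are counted from T1.

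**The plan's own figure.** 7 + 21 = 28 days, so the stated window length reproduces.

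**Step 1: share of the baseline period that can fall after intake.** Share = s/90, where s is days from intake to T1.

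- Residential: 14/90 = 15.6%.
- Outreach: 28/90 = 31.1%.
- With a 91.3-day quarter: 15.3% and 30.7%.
- With the strict limits of criterion 4 (13 and 27 whole days): 14.4% and 30.0%.

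These are ceilings. They count from intake, and support planning starts at or after intake.

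**Step 2: effect on the comparison.** Suppose (an assumption, not a protocol figure) that the daily rate of use is r before intake and kr from intake on.

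- Recorded before total: r[(90 − s) + ks].
- After total over 90 days: 90kr.
- Recorded difference: r(k − 1)(90 − s), against a true 90r(k − 1). The absolute change shrinks by the fraction s/90, whatever k is.
- Recorded ratio: 90k / [(90 − s) + ks].

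| True ratio k | s = 14 | s = 28 |
|---|---|---|
| 0.5 | 45/83 = 0.54 | 45/76 = 0.59 |
| 1.5 | 135/97 = 1.39 | 135/104 = 1.30 |
| 2 | 180/104 = 1.73 | 180/118 = 1.53 |

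If use does not shift at intake (k = 1), there is no dilution.

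**Step 3: length of the follow-up recall.**

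| Form | Shortest (days) | Longest (days) | Relative to 90 |
|---|---|---|---|
| T2 | 90 − 7 = 83 | 90 + 21 = 111 | 0.92–1.23 |
| T3 after T2 | 173 − 111 = 62 | 201 − 83 = 118 | 0.69–1.31 |
| T3, T2 missed | 180 − 7 = 173 | 180 + 21 = 201 | 1.92–2.23 |

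On schedule the first two are 90 days, equal to baseline. The ranges are extremes for one participant. If interviews were spread evenly over the window (an assumption), the mean shift would be (−7 + 21)/2 = +7 days. Mean recall would then be 97 days at T2 (97/90, about +8%) and 90 days between T2 and T3.

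**The case against.** The best case for the plan has four parts.

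- **The timing is disclosed.** Section 8(a) describes baseline as at or soon after the onset of support, so late baseline is a known feature of every T1 measure. This stands, but it does not settle the matter. A symptom score at T1 is one reading taken slightly late, whereas the AD-SUS adds up a period that could have been ended at intake, and section 21 names its comparison as before against after.
- **Advocacy itself is not miscounted.** It is micro-costed separately, so its cost does not enter as baseline cost. This stands. The dilution needs a shift in other health and social care use soon after intake, and the protocol gives no figure for one.
- **Unequal length can be rescaled.** Conversion to a common period is ordinary analysis-plan content, and that plan is not at hand. No text says raw totals will be compared. This stands, so the unequal lengths are a secondary point and not an error in the protocol.
- **Moving the anchor alone would lose data.** If baseline recall ended at intake while T2 recall still began at T1, up to 14 or 28 days would be on neither form. This is right, and the fix must cover that gap.

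A reader might also infer from section 14 that about 25% of participants would show doubled use at T3. The document does not support that. The 25% is planned loss by T2, followed by a further 25% loss (450 × 0.75 × 0.75 = 253, against 250 required). That arithmetic counts nobody who misses T2 and returns, and the protocol gives no number for such people.

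**Conclusion.** The point holds as a cheap improvement, minor to moderate in weight. The baseline AD-SUS period can contain up to about 15–16% (residential) or 31% (outreach) post-intake time, and the absolute before-and-after change is diluted by up to the same share. This rests on the rate of service use shifting at intake and staying shifted, and on interviews at the latest permitted day; earlier interviews or a smaller shift reduce it. Rescaling does not remove it.

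The variable length of follow-up recall is secondary. On schedule the periods are nominally equal, and the only large departure is the 173–201 days at T3 after a missed T2.

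Two stronger readings are tempting and go too far. The recall periods do not overlap one another: baseline recall ends at T1 and follow-up recall starts there, so the overlap is between baseline recall and the first days of support. Nor does the protocol name residential versus outreach as a service characteristic for the cost analysis; section 21 links service characteristics to quality of life and QALYs.

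The effect is limited to an exploratory secondary analysis. The CORE-OM outcome and the sample size are untouched.

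**What to change.** 1. Anchor the baseline AD-SUS to the three months before NGO intake. The timing of intake must already be known to apply criterion 4 and the section 13 limits.
2. Ask about use from intake to T1 as a separate short period and count it with follow-up, so that no days are lost.
3. Express before-and-after change in use and cost per 90 days of actual recall, from the intake and interview dates. Step 2 makes this more necessary, because intake to an on-schedule T2 can then last up to 14 + 90 = 104 or 28 + 90 = 118 days.
4. Flag T3 forms completed after a missed T2, report how many there are, and repeat the comparison without them.

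Cost: one extra recall item, and a baseline question that reaches back up to 104 or 118 days from the interview instead of 90, with somewhat more recall error. The rate calculation uses dates the study needs anyway. Where baseline forms have already been completed under the current wording, report the intake-to-T1 interval by support type and say that the baseline period includes early support.

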- 2. Evaluate whether aspects of the advocacy intervention experience thought to improve outcomes modify the effect of the advocacy intervention on mental health and wellbeing; in particular, to test whether
 - a. the effect changes as the amount of support received increases
 - b. the effect varies according to structural or service characteristics of NGOs;
- 3. Assess the service use and costs associated with advocacy interventions for trafficked people who have been referred into NGO services

8. (a) Study design

Exploratory prospective uncontrolled cohort study and realist evaluation with assessments at baseline (T1) (i.e. at or soon after onset of advocacy support), at 3 months follow up (T2) and at 6-months follow-up (T3). The primary outcome is reduced psychological distress (measured using the CORE-OM) at 3 months follow up (T2) compared with baseline (T1).

(b) Rationale for not including a control group

It is not feasible to recruit a control group for the following reasons: (1) All trafficked people who enter the National Referral Mechanism (NRM) are entitled to government-funded NGO support. Support is provided by a national network of NGOs; there is enough capacity, so NGOs do not operate waiting lists that could serve as a source of controls; (2) Trafficked people who enter the NRM but elect not to receive NGO support are extremely difficult to identify for recruitment. The PI's previous research showed that it is not feasible to recruit from settings such as the NHS and Local Authorities (4).

This study will therefore assess whether mental health among survivors of trafficking improve over the period during which advocacy support is provided, with measures taken at or soon after onset of advocacy intervention, at 3 months follow up, and at after a further 6 months follow up. To support the interpretation of any detected change as a causal intervention effect in the absence of a control group dose-response relationships between change over time and

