factors describing the intervention experience will be assessed. Such factors are the "dose of support" which will quantify by frequency and duration of support and "intervention characteristics" (while all NGOs provide advocacy-based support, the structural characteristics of services and the relative emphasis placed on components of support provided vary - reports of the National Audit Office and Public Accounts Committee, and conversations with NGOs, indicate considerable variability between services (9, 18).). Participant characteristics that predict outcomes will also be identified and dose-response analyses will be adjusted for their potential confounding effect.

9. Study setting

A total of six of the 12 NGOs providing government-funded advocacy interventions to survivors of trafficking in England have been purposively selected for variation in structural characteristics and service model. Participating organisations are as follows:

- 1. Ashiana
- 2. BAWSO
- 3. Hestia
- 4. Medaille Trust
- 5. Migrant Help UK
- 6. Salvation Army Accommodation Services

10. Eligibility criteria

Study 1 – Cohort Study

Inclusion criteria

To be eligible for inclusion in the study, participants must meet all inclusion criteria:

- 1. Be aged 18 years or older;
- 2. Have entered into the UK National Referral Mechanism;
- 3. Have consented to receive advocacy support from a participating non-governmental organisation (NGO);
- 4. At date of baseline interview, have received fewer than 14 days' residential advocacy support or 28 days' outreach advocacy support from any NGO through the UK National Referral Mechanism;
- 5. No longer be being exploited by their traffickers.

If the participant has undergone an age determination procedure (i.e. is age-disputed), the participant's age as confirmed by the local authority should be used.

Exclusion criteria

People will be excluded from the study if they:

1. Do not have the capacity to provide consent to participate in the studies, including because of learning disability, psychotic illnesses or severe drug or alcohol problems.

Eligibility will be assessed by trained NGO staff members referred hereafter as "NGO Researchers".

Study 2 - Qualitative study

Inclusion criteria

Survivors- To be eligible for inclusion, survivors must meet the inclusion criteria for the above cohort study and additionally have consented to participate in the qualitative study. English language proficiency is not a selection criterion.

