The "dose of the support received" will be quantified (e.g. duration in terms of session length, frequency, and the period over which sessions are received; structural and service characteristics NGOs) and change scores will be regressed on this dose. Possible confounders of the dose-response relationship will be identified by testing whether any baseline participant characteristics (e.g. gender, immigration status) predict change over time. Any such potential confounders will then be adjusted for in a second step which regresses the change changes on the dose variable and the putative confounders.

These analyses (which do not include a control group) are based on the assumption that a control group would not exhibit any change over the intervention period. In order to assess the

impact of departures from this assumption on the evaluation of the advocacy support intervention sensitivity analyses will be conducted. Literature evidence will be used to generate a possible distribution of mean outcome change in a hypothetical control group of eligible trafficked woman waiting to start the support program (37); and will then include such sensitivity parameters in our analyses models to study their impact on the estimation of the prepost effect.

20c Methods for handling missing data

In the case of missing data in the CORE-OM outcomes, putative baseline confounders, or process variables, multiple imputation (MI) will be used to ensure that the analyses remain valid under an appropriate missing at random assumption. This will enable us to (multiply) impute realistic outcome patterns including allowing for process variables such as discontinuation of advocacy support to drive loss-to follow-up.

21. Economic evaluation

An exploratory analysis of service use, costs and effects before and after intervention will be undertaken with the results presented using a cost consequences framework, which is recommended for the evaluation of complex interventions that have multiple effects (38). This work will be used to support the generation of recommendations for future research and the development and testing of economic measures appropriate for this population. Specific objectives will include the following:

- 1. Calculate the cost of the advocacy interventions taking a micro-costing (bottom-up) approach (38).

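### T1 follows the start of support by up to 14 days (residential) or 28 days (outreach) from intake, which can bias the objective 2 comparisons unless the lag enters the models

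*Protocol*

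**What the plan says.** - **Start of the intervention.** Section 11: "The intervention is considered to commence at the initiation of the individual support planning process".
- **Timing of T1.** Section 13 says the baseline questionnaire "will take place after commencement of individual support planning (i.e. start of intervention", and sets the limit by service mode. The residential limit is "within two weeks of intake into NGO support services (for clients receiving residential advocacy support". The outreach limit is twice as long: "within 4 weeks of intake (for clients receiving outreach advocacy support". Inclusion criterion 4 in section 10 mirrors this: at T1 participants must "have received fewer than 14 days' residential advocacy support or 28 days' outreach advocacy support". Section 8 describes T1 as "at or soon after onset of advocacy support".
- **Timing of follow-up.** T2 is at +90 days and T3 at +180 days, with "A 28 day window, defined as 7 days before and 21 days after the due date". The event from which the days are counted is not stated. Section 14 describes T2 and T3 as following 3 and 6 months of support.
- **Objective 2 analysis.** Section 20b builds change scores over the intervention period, and "change scores will be regressed on this dose", where dose also covers NGO structural and service characteristics. Adjustment is limited to baseline participant characteristics that are found to predict change. Dose comes from client records (section 12).
- **Role of the analysis.** Section 8(b) relies on dose-response to support a causal reading, because there is no control group.

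**The concern.** T1 always falls after the defined start of the intervention, and the permitted delay for outreach clients is twice that for residential clients. Any improvement before T1 is already in the T1 score and drops out of the change. If more is lost in one service mode than in the other, a service characteristic that correlates with mode can appear to modify the effect when it does not.

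Dose has a related problem. If sessions before T1 count, they add to the predictor while their effect is missing from the outcome.

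The protocol does fix how confounders are chosen, by a test of whether they predict change. Days of support before T1 is not among the eight additional baseline measures in section 12. The only sensitivity analysis in section 20b concerns change in a hypothetical control group, not the timing of T1. At stake is objective 2, which carries the causal argument.

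**Working it through.** **1. The plan's own figures.** From section 14: 450 × 0.75 = 337.5 participants at T2; d = 0.18 and SD = 18 give 0.18 × 18 = 3.24 points. A two-sided 5% paired t-test with n = 337 and d = 0.18 has 90.9% power. The T2 figures reproduce and are not in dispute; 3.24 points serves below as the reference change.

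**2. Lag inputs.** The limits are 14 and 28 days from intake (section 13), or 14/90 = 16% and 28/90 = 31% of a 90-day period. The protocol gives no recovery curve, so the curves below are assumptions.

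**3. T2 at T1+90 days, linear change.** Both groups are observed for 90 days at the same slope. Spurious gap: 0%.

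**4. T2 at T1+90 days, exponential recovery.** Let y(t) = D(1 − exp(−kt)), with k = ln 2 / h and h the half-life. The change from T1 at day t0 is D·exp(−k·t0)·(1 − exp(−90k)). With everyone at the limit, the outreach/residential ratio is exp(−28k)/exp(−14k) = exp(−14k).

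| Half-life h (days) | Ratio | Gap |
|---|---|---|
| 30 | 0.724 | 27.6% |
| 45 | 0.806 | 19.4% |
| 60 | 0.851 | 14.9% |
| 90 | 0.898 | 10.2% |

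If residential change is 3.24 points, the gap is 3.24 × 0.102 = 0.33 to 3.24 × 0.276 = 0.89 points. If 3.24 is instead the change from day 0, it is 2.91 − 2.61 = 0.30 (h = 90) to 2.34 − 1.70 = 0.65 points (h = 30). Mid-window (day 7 against day 14) the ratio is exp(−7k), 0.948 to 0.851, a gap of 5% to 15%. The upper end depends on the assumed half-life: h = 14 would give a ratio of 0.50.

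**5. The 90 days counted from intake.** Under linear change the observed spans at the limits are 90 − 14 = 76 and 90 − 28 = 62 days, and 1 − 62/76 = 18%. With exponential recovery as well, the shares of the first-90-day change still captured are 0.796 and 0.612 (h = 90) or 0.684 and 0.456 (h = 30). The gap is then 1 − 0.612/0.796 = 23% to 1 − 0.456/0.684 = 33%.

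**6. Size against sampling error.** Assume an equal residential/outreach split of 337 and an SD of change of 18, as the plan's own conversion implies. The standard error of the difference in mean change is 18 × √(2/168.5) = 1.96 points. The step 4 gap is 0.33/1.96 = 0.17 to 0.89/1.96 = 0.45 standard errors.

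**7. Dose slope.** Suppose dose is pre-T1 plus post-T1 support, and T1–T2 change depends on post-T1 support only, with slope β. Write V for variances and C for the covariance of the two parts. The expected slope on total dose is β(Vpost + C)/(Vpost + Vpre + 2C). This is below β if C > −Vpre and above it if C < −Vpre. The protocol gives neither quantity and does not say whether pre-T1 support counts, so no direction follows.

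**The case against.** The strongest reply is that bias is possible but not shown.

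- The 14 and 28 days are maxima counted from intake, while support starts at planning, after a needs assessment. A reader might infer that outreach clients are in fact interviewed twice as late; the protocol gives no actual lags. This stands.
- With T2 at T1+90 days and steady change the gap is zero. This stands, so the range must start at 0%.
- Even at the limits the step 4 gap is under half a standard error. This stands as to practical size. A systematic component is still worth removing from the analysis on which the causal reading rests.
- Residential versus outreach is not a named contrast under objective 2b. An NGO-level comparison is affected only as far as NGOs differ in service mix. This stands.
- The screen in section 20b covers any baseline characteristic, with examples only, so it is too strong to say that it could not pick up the lag. This stands, but selection would then hang on a significance test, and the lag is not listed for testing.
- The dose-counting window is the kind of detail a statistical analysis plan may settle. This stands, and the missing window alone would be no finding. The confounder rule, by contrast, is written into the protocol.
- T1 is openly described as soon after onset, the lag is capped, and the study is exploratory. If early change is improvement, losing it makes the primary T1–T2 test conservative. This stands: the point concerns objective 2 and does not show a spurious primary result.

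**Conclusion.** The concern holds as a possible bias in objective 2, not as a demonstrated one. T1 follows the start of support, the permitted lag depends on service mode, and the stated adjustment rule does not guarantee that the lag is handled.

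Differential loss requires front-loaded change or follow-up counted from intake. With T2 at T1+90 days and everyone at the window limit, the spurious gap is 0% under linear change and 10–28% under exponential recovery with half-lives of 90 to 30 days, or roughly 0.3–0.9 CORE-OM points on 3.2. An intake anchor gives 18% under linear change and 23–33% when combined with the same curves. All of these rest on assumed trajectories.

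A reader might infer that outreach will look less effective, or that the dose slope will be flattened. The document supports neither as a prediction: actual lags, the service mix across NGOs and the dose window are not given. The change is worth making because it is cheap and protects the plan's main causal argument.

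**What to change.** In section 20b:

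- Derive days of support before T1 as a number. Inclusion criterion 4 already requires this to be established; state the date from which it is counted, because the start of support planning is not listed among the routinely recorded items.
- Force it into the objective 2 dose and service-characteristic models, outside the screen for predictors of change.
- Count dose from T1 to the outcome visit and enter pre-T1 support as a separate covariate.
- Show T1–T2 change by days to T1.

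In section 13, state that the T2 and T3 due dates are counted from T1.

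The cost is analysis wording, one or two derived variables and one or two degrees of freedom, with about 250 or more expected completers. One limit remains: under the stated windows, lags over 14 days occur only in outreach clients, so adjustment in that range relies on the model rather than on overlap between service modes.
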